6.3.2 Up-dosing (also Referred to as Buildup or Escalation) Visits

The Up-dosing Period will last approximately 20 (to a maximum of 40) weeks and comprise 10 scheduled up-dosing visits (including the first 300 mg dose of the Maintenance Period), with the potential for unscheduled visits for assessment of dose tolerability, dose-reduction, dose re-escalation, or management of AEs.

Subjects will return to the clinic every 2 weeks for up-dosing to a maximum daily dose of 300 mg. The first dose of study product at each new dose level will be administered in the CRC under direct observation and medical supervision.

Subjects must be free from active wheezing, a flare of atopic disease (eg, atopic dermatitis), or suspected intercurrent illness prior to any dose escalation. Subjects should be maintained on their current, or a reduced, dose level of study product until their flare of asthma, atopic disease, or intercurrent illness has resolved.

Subjects should withhold their daily home dose of study product on in-clinic dosing days, but should take all other prescribed medications as scheduled.

The following assessments/procedures are scheduled for each up-dosing visit in the CRC:

- Concomitant medication review
- Diet (food allergen exposure) history update
- Return unused capsules to the clinic at each visit
- Symptom-directed physical examination
- Pre-dose vital sign measurement (blood pressure, pulse rate, body temperature)
- PEFR (3 attempts are to be performed, and the best value taken). PEFR should be measured at the same time for each visit assessment.
- Study product administration under observation in the clinic
- Post-dose vital sign measurements (blood pressure, pulse rate) within 15 to 30 minutes postdose, and at 15- to 30-minute intervals thereafter for the postdose observation period
- Take home capsules for daily dosing until next visit
- Monitoring for compliance
- Monitoring for adverse events, including allergic symptoms (see below and also Section 6.7 and Section 7.2)
- Subjects will be reminded to continue to follow a peanut-avoidant diet for the duration of the study.

Subjects enrolled in the optional saliva substudy (North America sites only) who are not experiencing gastrointestinal symptoms will have a saliva sample collected on the morning of an early up-dosing visit (6 weeks \pm 2), according to Table A6 in Appendix 6.

At a minimum, subjects must be observed for 1½ hours after dose administration, with vital sign measurements and assessment for signs and symptoms of allergic reaction performed every 30 minutes. Any signs or symptoms of allergic reaction will be recorded in the CRF on the appropriate Dosing Symptom/AE form.

If up-dosing is completed with no symptoms detected after 1½ hours of post-dose observation, the subject may be sent home from the CRC. If the subject exhibited mild symptoms, the duration of the observation period should be extended to a minimum of 1 hour after resolution of the symptoms. For moderate symptoms, the observation period should be extended to a minimum of 2 hours after resolution of the symptoms. And for severe symptoms, the subject should be observed for a minimum of 3 hours after resolution of the symptoms, either at the CRC or an emergency facility, as appropriate.

Any subject deemed to have severe symptoms that include hypoxia, hypotension, or change in mental status (stage 3 anaphylaxis defined in **Appendix 3**), or who receives intensive therapy (to be determined by the investigator, but may include such interventions as IV epinephrine,

intubation, or admission to an intensive care unit) for an allergic reaction at any time should be discussed with the Medical Monitor and discontinued from the study.

On the day following in-clinic up-dosing, the site is to make telephone contact with the subject/subject's parent or guardian to enquire if any AEs (including allergic symptoms) occurred subsequent to the subject leaving the clinic, and to provide assistance in the recording of any such events in the diary.

A dose escalation attempt may be postponed 1 to 2 weeks if, in the clinical judgment of the investigator, the current dose level has not been sufficiently well tolerated to proceed to the next dose level. Further, if an investigator suspects that a subject has not tolerated, or is not tolerating, his or her current dose level, the investigator should have the subject return to the clinic to determine whether a dose reduction is warranted, and if so, the magnitude of the reduction. Guidelines for setting the new, lower, dose are outlined in Section 6.7.5, with the dose adjustment depending on the severity of the dose-related symptoms.

Subjects who require dose reduction during a 2-week dosing period will have their escalation schedule reset, as necessary, to maintain the new dose level for a 2-week period prior to attempting to re-escalate.

Following a dose reduction, it is advised that an escalation attempt be made by 4 weeks, unless escalation is to be delayed further due to administration of epinephrine, as defined in Section 6.7. Failure to successfully escalate after 3 consecutive attempts, with each attempt spaced at least 2 weeks apart, will result in the cessation of dosing and the subject being considered an escalation failure and nonresponder. The subject will be asked to return to the CRC 14 days following the last dose of study product to undergo an Early Discontinuation Visit (Section 6.5) and is to be followed for safety in the interim.

For symptoms occurring during the Maintenance Period, the same study dosing rules and guidelines that apply for the Up-dosing Period will also apply.

6.3.3 Up-dosing Midpoint Visit

The first 80 mg in-clinic dosing visit is the approximate midpoint of the Up-dosing Period. At the up-dosing visit for the first administration of the 80 mg dose of study product the following procedures are to be performed in addition to those performed at the other up-dosing visits:

- Complete (not just symptom-directed) physical examination, including height and weight
- Assessment of asthma control in asthmatic subjects using the Asthma Control Test questionnaire
- Urine pregnancy test, for females of childbearing potential
- Review with subjects and parents or guardians teaching about food/peanut allergy according to the investigational site's established standards. This is to include at a minimum the following topics (some or all of which may be addressed in a comprehensive anaphylaxis action plan):
 - Recognition of an allergic reaction and of the symptoms of anaphylaxis

- When and how to administer epinephrine via auto-injector
- Requirement to go to nearest emergency facility following use of epinephrine auto-injector
- Ways to minimize the risk of accidental exposure to peanut in, and outside of, the home (may be supplemented by referral to recognized food allergy organizations for access to additional learning materials)

6.3.4 End of Up-dosing / Start of Maintenance Period Visit

The first 300 mg in-clinic dosing visit is the end of the Up-dosing Period; it is also the start of the Maintenance Period. At this visit the following procedures are to be performed in addition to those performed at the up-dosing visits:

- Complete (not just symptom-directed) physical examination, including height and weight
- Assessment of asthma control in asthmatic subjects using the Asthma Control Test questionnaire
- Urine pregnancy test, for females of childbearing potential
- Blood draw to collect samples for:
 - Peanut- and peanut-component specific IgE, total IgE, and peanut- and peanutcomponent specific IgG4 (immunoglobulin assays). The amount of blood to be taken for the immunoglobulin assays will be communicated from the central laboratory and included in the manual of procedures.
 - CBC, obtained with the same venipuncture as the blood draw for the immunoglobulin assays
 - Optional exploratory immune cell characterization by the Immune Tolerance Network (ITN). Note that these samples can be obtained with the same venipuncture as the blood draw for the immunoglobulin assays and CBC, but will require an addition volume of blood to be collected. Separate informed consent is required.

The amount of blood to be taken in total for the above assays (required immunoglobulin assays, required CBC, and optional immune cell characterization assays) will not exceed a total volume of 0.67 mL/kg in children, to a maximum of 50 mL, total, in 8 weeks. Blood draw should be collected in compliance with local laboratory guidelines and testing regulations.

- Skin prick test to peanut extract
- Review with subjects and parents or guardians teaching about food/peanut allergy according to the investigational site's established standards. This is to include at a minimum the following topics (some or all of which may be addressed in a comprehensive anaphylaxis action plan):
 - Recognition of an allergic reaction and of the symptoms of anaphylaxis
 - When and how to administer epinephrine via auto-injector

- Requirement to go to nearest emergency facility following use of epinephrine auto-injector
- Ways to minimize the risk of accidental exposure to peanut in, and outside of, the home (may be supplemented by referral to recognized food allergy organizations for access to additional learning materials)

For the first 2-week dosing interval at the 300 mg/d maintenance dose, the dose will be administered from 300 mg capsules. Thereafter, 300 mg doses may be administered from foil-laminate sachets.

6.3.5 Maintenance Period Visits

The Maintenance Period begins with the first 300 mg in-clinic dosing visit.

The first visit in the Maintenance Period is to occur 2 weeks after the start of dosing at 300 mg/d; thereafter Maintenance Period visits will occur approximately every 4 weeks.

Subjects should withhold their daily home dose of study product on in-clinic dosing days, but should take all other prescribed medications as scheduled.

The following assessments/procedures are scheduled for each in-clinic dosing Maintenance visit in the CRC:

- Concomitant medication review
- Diet (food allergen exposure) history update
- Return unused sachets or capsules to the clinic at each visit
- Symptom-directed physical examination
- Pre-dose vital sign measurement (blood pressure, pulse rate, body temperature)
- PEFR (3 attempts are to be performed, and the best value taken). PEFR should be measured at the same time for each visit assessment.
- Study product administration under observation in the clinic
- Postdose vital sign measurements (blood pressure, pulse rate) within 15 to 30 minutes postdose, and at 15- to 30-minute intervals thereafter if the postdose observation period is prolonged beyond the requisite 30 minutes (see below).
- Take home sachets (or capsules, as appropriate) for daily dosing until next visit
- Monitoring for compliance
- Monitoring for adverse events, including allergic symptoms (Section 6.7 and Section 7.2)
- Subjects will be reminded to continue to follow a peanut-avoidant diet for the duration of the study.

In the event that dose reduction from the stable dose of 300 mg/d is required during the last weeks of the planned 24-week Maintenance Period, the Maintenance Period may be extended on

an individual basis up to an additional 4 weeks (to a maximum of 28 weeks) or to a maximum study duration of 68 weeks, whichever is shorter. The Exit DBPCFC must be performed by Study Week 68. Additionally, subjects must maintain a dose of 300 mg/d for at least the last 2 consecutive weeks of the Maintenance Period to qualify for the Exit DBPCFC. Failure to do so will result in the subject being discontinued from the study as a maintenance failure nonresponder for the primary and key secondary analyses.

If dosing is discontinued, the subject will be asked to return to the CRC 14 days following their last dose of AR101 to undergo an Early Discontinuation Visit (Section 6.5).

The procedures for dose reduction and re-escalating back to a dose of 300 mg/d in the Maintenance Period will follow the same guidelines as for the Up-dosing Period.

The procedure for monitoring subjects for safety after in-clinic dosing is the same as for updosing visits (Section 6.7.3), except that the initial period of required post-dose observation may be shortened to 30 min.

6.4 Unscheduled Visits / Unscheduled Blood Draws

The procedures performed at Unscheduled Visits may include any or all of those performed at Up-dosing Visits.

Additionally, if a subject (subject's parent/guardian) declares his or her intention to discontinue study product dosing, whether at a scheduled visit or an unscheduled visit, a blood draw should be performed to obtain a CBC, immunoglobulin assays, and optional exploratory immune cell characterization samples (if the subject is participating in the substudy). If a blood draw is performed at this time, it will take the place of the Exit Visit / Early Discontinuation Visit blood draw (Section 6.5).

6.5 Exit Visit / Early Discontinuation Visit

Subjects who tolerate 300 mg/d and are maintained at this dose for approximately 24 weeks will return to the clinic for an Exit Visit.

Subjects who fail initial escalation or up-dosing, or who prematurely discontinue treatment, will return to the site for an Early Discontinuation visit that consists of the same procedures as the Exit Visit, but without a DBPCFC. An Early Discontinuation Visit is to occur 14 days from the last dose of study product.

Subjects who withdraw from ARC003 wholly or in part due to intolerable gastrointestinal symptoms, who are not enrolled in the optional saliva study, may be approached at the time of their early termination visit to provide voluntary consent to enroll and participate in the saliva substudy (North America sites only). If this occurs, such subjects will provide a saliva sample as part of the early termination visit and then again during post-OIT follow-up (Table A6 in Appendix 6).

The following procedures will be performed at the Exit/ Early Discontinuation Visit:

• Concomitant medication review

- Diet (food allergen) history
- Completion of the palatability questions
- Completion of the food allergy related quality of life questionnaire (FAQLQ), and the food allergy independent measure (FAIM) questionnaire after the completion of the exit DBPCFC and unblinding for all the patients
- Completion of the Treatment Satisfaction Questionnaire for Medication (TSQM-9) and the exit questionnaire after after the completion of the exit DBPCFC and unblinding for all the active subjects
- Assessment of asthma control in asthmatic subjects using the Asthma Control Test questionnaire
- Physical examination, including weight and height
- Vital signs (blood pressure, pulse rate, body temperature); if DBPCFC is to be conducted, these vital sign measurements should be taken shortly before the first challenge dose
- PEFR (3 attempts are to be performed, and the best value taken). PEFR should, to the extent possible, be measured at the same time as for prior visit assessments.
- Urine pregnancy test, for females of childbearing potential
- Blood draw to collect samples for:
 - Peanut-and peanut-component specific IgE, total IgE, and peanut- and peanutcomponent specific IgG4 measurement (immunoglobulin assays. The amount of blood taken for the immunoglobulin assays will be communicated from the central laboratory and included in the manual of procedures.
 - CBC, obtained with the same venipuncture as the blood draw for the immunoglobulin assays
 - Optional exploratory immune cell characterization by the Immune Tolerance Network (ITN). Note that these can be obtained with the same venipuncture as the blood draw for the immunoglobulin assays. Separate informed consent is required.

The amount of blood to be taken for the above assays (required immunoglobulin assays, required CBC, and optional immune cell characterization assays) be will not exceed a total volume of 0.67 mL/kg in children, to a maximum of 50 mL, total, in 8 weeks. Blood draw should be collected in compliance with local laboratory guidelines and testing regulations. (For subjects who are withdrawing prematurely from the study due to an AE, the blood draw at the Early Discontinuation Visit can be foregone if it was performed at the time that dosing with study product ceased.)

- Skin prick test to peanut extract
- Take home sachets (or capsules, as appropriate) for daily dosing until next visit (if enrollment in ARC004 does not happen at this visit)
- Monitoring for compliance
- Monitoring for AEs, including allergic symptoms (Section 6.7 and Section 7.2)

In addition to the procedures listed above, eligible subjects will have an Exit DBPCFC performed. Eligible subjects are those who tolerate 300 mg/d and are maintained at this dose for the approximately 24-week Maintenance Period. The Exit DBPCFC is to be conducted in accordance with PRACTALL guidelines, with the protocol-specified modifications, as described in Section 6.6.2.

Each subject participating in the study will be unblinded when he/she completes the Exit Visit procedures (including the Exit DBPCFC for eligible subjects), provided regulatory and IRB/EC approval for ARC004 have been received, the availability of IP for ARC004, and all major data queries for the subject have been resolved (Section 3.3). If this is not the case, the subject shall remain on blinded treatment until these requirements are satisfied. The subject should continue his or her maintenance visits (completed as unscheduled visits), every 30 days, and complete all protocol procedures at each visit until study completion and rollover to ARC004.

The end of the study is defined as the date of the last visit of the last subject.

All ARC003 placebo subjects who complete the study are eligible for rollover into the ARC004 protocol. Former ARC003 placebo subjects in ARC004 will undergo an escalation schedule identical to that for active subjects in the ARC003 protocol. All subjects on active treatment (AR101) in ARC003 who pass the DBPCFC at the 300 mg (443 mg cumulative) challenge dose level of peanut protein are eligible to proceed to ARC004. Those who do not pass DBPCFC at the 300 mg (443 mg cumulative) challenge dose level will be considered endpoint failures and nonresponders for the primary analysis. They will not be eligible for rollover into the ARC004 protocol due to safety concerns. Those subjects who pass DBPCFC at the 300 mg (443 mg cumulative) challenge dose level, will be also be considered endpoint failures and nonresponders for the primary analysis for North America or Europe, respectively; however, they will be eligible for rollover into the ARC004 protocol because tolerating a 300 mg (443 mg cumulative) dose of peanut protein is considered a clinically relevant level of desensitization.

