- p) FAQLQ and FAIM to be filled up prior to screening DBPCFC and after exit DBPCFC and unblinding
- q) Palatability questions to be answered before the exit DBPCFC for all patients
- r) TSQM-9 and Exit questionnaire to be answered after exit DBPCFC and unblinding for all active patients

- s) Subjects under the age of 18 years who fall into any of these 3 categories will be asked to fill out the PEESSTMv2.0 questionnaire (Franciosi et al., 2011), with the assistance of a parent or guardian, as appropriate, every month for 6 months:
 - Any subject whose dose is withheld for > 7 days due to GI AEs and resumes dosing at a reduced dose level (Section 6.7)
 - Any subject who develops chronic/recurrent GI AEs at or before reaching the 20 mg dose level and resumes dosing after a 30-day dosing hiatus (Section 6.7.3.2)
 - Any subject who permanently discontinues dosing who had experienced GI AEs (Section 4.3.2)

Note: BP = blood pressure; PR = pulse rate; temp = body temperature; OIT = oral immunotherapy; DBPCFC = double-blind, placebo-controlled food challenge

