# Figure 2.1 Illustration of study design

Ref. protocol: Figure 3–1. Study Design

Table 2.1	Study d	esign info	rmation,	treatment	regimens
-----------	---------	------------	----------	-----------	----------

Phase of Development	3
Randomized Trial	Yes
Stratification Factors	Age Group:
	LT: Less than 18 years of age,
	GT: Equal to or more than 18 years of age
	Geographic Region:
	NA: North America,
	EU: Europe
No. Treatment Arms	2
No. of Subjects	500 planned per the protocol; actual enrollment is 555
Treatment Groups and	AR101 (peanut protein), placebo
Ratio	= 3:1

Investigational Product, Dosage, and Administration	AR101 (peanut protein) The initial dose escalation (first 2 days) includes doses of 0.5 mg up to 6 mg followed by 2 weeks at 3 mg. Future dose escalations will occur every 2 weeks with the escalation administered in the clinical research center. Doses will be escalated up to the subject's first in- clinic dose at 300 mg, ideally 20 weeks in duration, but may be extended to a maximum of 40 weeks to accommodate dose reductions and re-escalations, if necessary. The Maintenance Period starts with the first home dose of 300 mg. Ideally, it will be 24 weeks in duration, but it may be extended by up to an additional 4 weeks (for a maximum Maintenance Period duration of 28 weeks), or to a total Treatment Phase duration of 68 weeks, whichever occurs first, to accommodate dose reductions and re-escalations that may occur during the final weeks of the Maintenance Period.
Reference Therapy, Dose, and Administration or Comparative Intervention	Placebo: AR101 matching placebo on the same schedule

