#### 6.2. SUBGROUP ANALYSES

The primary analysis of efficacy and safety data will be performed in pediatric subjects ages 4-17. Additional analysis will be performed using the following subgroups of age, geographic region, or both age and geographic region.

Age Group:

- Ages 4-11 Years
- Ages 12-17 Years
- Ages 18-55 Years
- Ages 4-55 Years

Geographic Region:

- North America (NA)
- Europe (EU)

For countries with at least 3 subjects in each treatment arm, subgroup analyses may be performed by country.

In select analyses, age group and/or region will be included as factor(s) in the statistical analyses. When any region has fewer than 3 subjects with an evaluable response for the variable of interest in either treatment arm, region will be excluded from the model.

In addition to subgroup analyses described above, additional population subsets may be defined and utilized for select analyses. These subsets will include the following:

Baseline ps-IgE:

- $< 100 \text{kU/L} \text{ versus} \ge 100 \text{kU/L}$
- Cutoff predictive of screening MTD ≤30 mg (as determined from the Screened Population, see Section 9.6.6.)

Baseline SPT wheal diameter:

- < 8mm versus  $\ge 8$ mm
- Cutoff predictive of screening MTD ≤30 mg (as determined from the Screened Population, see Section 9.6.6)

Additional subgroups for ps-IgE and SPT wheal diameter may be defined (e.g., those predictive of subjects who fail to reach the target dose of 300 mg, see Section 9.6.7) and evaluated in exploratory analyses. These will be described as such in the study report.

Other subgroups:

- Asthmatic subjects
- Subjects enrolled in protocol ARC004

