# 9.6. EXPLORATORY ANALYSES

#### 9.6.1. Treatment Satisfaction

Assessment of treatment satisfaction will be performed using the Treatment Satisfaction Questionnaire for Medication (TSQM-9), an exit survey including palatability questions.

The TSQM-9 is a widely used instrument to assess treatment satisfaction with medication in studies where patient reported side effects have a potential to interfere with the objectives of the study. The instrument consists of 9 questions that comprise 3 scales.

Responses to the 9 individual items will be presented using descriptive statistics. The scale scores (effectiveness, convenience, and global satisfaction) will be calculated and summarized using descriptive statistics.

The Effectiveness scale includes items 1-3, the Convenience scale includes items 4-6, and the Global Satisfaction scale includes items 7-9. Each scale will be scored as: 100\*[(sum of non-missing responses) minus the number of non-missing responses] divided by the maximum possible score of the sum of non-missing responses. If more than one item within the scale has a missing result then the scale score will not be calculated.

Analysis of the scale scores will be performed using ANOVA models with terms for treatment group and region.

In addition to the TSQM-9, an exit survey will be performed at study exit. The survey includes questions on study drug palatability, frequency of taking study drug as instructed, impact on attending clinic visits, interest in continuing to take study drug, if the subject would recommend the study drug to others, and burden of treatment. Responses to each item will be summarized with descriptive statistics and type of instrument administered (parent or subject ages 12 and older). No statistical testing is planned for this questionnaire.

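### SAP 9.6.1 plans an ANOVA with a treatment-group term on the TSQM-9, but the protocol collects the TSQM-9 from AR101 subjects only

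*Protocol*

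**What the plan says.** Protocol 6.5 lists the procedures of the Exit/Early Discontinuation Visit. The TSQM-9 and the exit questionnaire come after "the completion of the exit DBPCFC and unblinding for all the active subjects". Appendix 1, footnote r, says the same: "TSQM-9 and Exit questionnaire to be answered after exit DBPCFC and unblinding for all active patients". Neighbouring items are not restricted in this way. Protocol 6.5 gives the FAQLQ and FAIM to all patients, and footnote q has "Palatability questions to be answered before the exit DBPCFC for all patients".

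SAP 9.6.1 plans descriptive statistics for the nine TSQM-9 items and for the three scale scores. It then adds: "Analysis of the scale scores will be performed using ANOVA models with terms for treatment group and region". It does not mention that only one arm answers. For the exit survey, described in the same section, it says: "No statistical testing is planned for this questionnaire".

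SAP 3.4 classes treatment satisfaction as an exploratory endpoint. SAP 6.5 lays out all summary tables by AR101 and placebo and makes no exception for the TSQM-9.

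**The concern.** The SAP commits to a between-arm model for an instrument that the protocol gives to one arm. A programmer who follows both documents reaches a model with no comparator.

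There are two ways this can go. If the data arrive as scheduled, no treatment effect or p-value exists, and someone must decide after unblinding what to report in its place. If a few placebo subjects fill in the form off schedule, the model runs. It then gives a p-value that sets AR101 subjects who finished the trial and know their treatment against a handful of placebo dropouts. The second outcome is worse, because nothing in the output would show that anything was amiss.

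**Working it through.** The documents give no figure of their own on this point, so there is none to reproduce. The check has two parts: who is planned to answer, and what the model can estimate.

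**1. Who answers, and what the SAP does with the answers**

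| Instrument | Planned respondents and timing (Protocol 6.5, Appendix 1) | SAP analysis |
|---|---|---|
| FAQLQ, FAIM | Both arms; exit forms after challenge and unblinding | Between-arm ANCOVA (9.5.6) |
| Palatability | Both arms, before the exit challenge | Descriptive, as part of the exit survey (9.6.1) |
| Exit questionnaire | AR101 only, after challenge and unblinding | Descriptive, no test (9.6.1) |
| TSQM-9 | AR101 only, after challenge and unblinding | Descriptive, plus ANOVA with a treatment term (9.6.1) |

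Only the last row pairs one-arm collection with a two-arm model. In Protocol 3.4 and 6.5, active subjects are set against placebo subjects, so the word identifies the AR101 arm.

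**2. How many placebo subjects are left out**

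SAP Table 2.1 gives "500 planned per the protocol; actual enrollment is 555" and a 3:1 ratio. Placebo subjects of all ages: 555 × 1/4 = 138.75, about 139. SAP 2.4 gives 499 subjects aged 4 to 17, so placebo children: 499 × 1/4 = 124.75, about 125. These are ceilings, because not every enrolled subject reaches an exit challenge. The planned TSQM-9 contribution from either group is 0.

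**3. What the model can estimate**

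For subject i, write score = μ + τ·T + ρ·R + error, with T = 1 for AR101, T = 0 for placebo, and R marking region.

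- With AR101 rows only, T = 1 throughout. Adding any constant c to μ and subtracting c from τ leaves every fitted value unchanged. Only μ + τ, the AR101 level, is identified; τ is not.
- In ranks: columns [1, T, R] have rank 2 of 3, and columns [1, R] also have rank 2. The numerator degrees of freedom for treatment are 2 − 2 = 0, so there is no F test.

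A numerical check on 400 illustrative rows, with about 30% in one region, agreed. AR101 only: 3 columns, rank 2, 0 placebo rows. Both arms at 3:1: 3 columns, rank 3, 109 placebo rows. The result does not depend on the regional split as long as both regions are present.

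**4. What one stray placebo form does**

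Take one AR101 row from each region, (1,1,0) and (1,1,1), and one placebo row, (1,0,0). The determinant is 1·(1·0 − 1·0) − 1·(1·0 − 1·1) + 0 = 1, which is not zero. The rank rises to 3 and τ becomes estimable on the strength of one placebo subject. The model will therefore not reliably fail in a way that alerts the analyst.

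**The case against.** **The SAP already describes the TSQM-9.** This is correct. Section 9.6.1 plans descriptive statistics for items and scales whatever happens to the ANOVA, so the error is one surplus sentence. That limits the size of the fix but does not make the sentence workable.

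**Placebo subjects may answer at the Early Discontinuation Visit.** Protocol 6.5 gives that visit the same procedures as the Exit Visit apart from the food challenge, and Appendix 1 marks the TSQM-9 in a column shared by both. Some forms could arise this way. But the TSQM-9 is tied to a completed exit challenge and to unblinding. The Early Discontinuation Visit has no challenge, and SAP 2.5 keeps discontinuers blinded until database lock. A placebo TSQM-9 form would thus fall outside the stated schedule and come from a selected group of dropouts. This argues for listing such forms, not for keeping the model.

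**It is only exploratory.** This is also correct, and it is why the point is minor.

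**A reader might go further and infer that region drops out as well**, leaving nothing in the model. SAP 6.2 sets a minimum count per region and arm: "fewer than 3 subjects with an evaluable response for the variable of interest in either treatment arm, region will be excluded from the model". Each region has 0 planned placebo responders. The documents do not support resting anything on this. The rule speaks of either treatment arm and so presupposes data from two arms. With AR101 rows alone, an intercept and a region term can still be fitted. Only the treatment term fails.

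**A reader might also infer that the FAQLQ and FAIM comparison is invalid**, because those exit forms too follow unblinding. They are planned in both arms, so the contrast is estimable. SAP 9.5 calls the other secondary endpoints supportive and rules out labeling claims. Unblinded self- or parent-report is a caveat for the study report. Pointing to the Completer analysis would not answer it, since Completers are the subjects who had the exit challenge and, on the protocol's schedule, answer after unblinding.

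**Conclusion.** The point holds for the treatment term. Three planned ANOVAs cannot deliver the comparison they specify, because the protocol plans no placebo TSQM-9 data. This rests on two readings: that active subjects means the AR101 arm, which the protocol's own usage supports, and that forms are collected as Protocol 6.5 and footnote r state. It needs no assumption about effect size, variance or regional split.

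The consequence is small. No primary, key secondary or other secondary test is touched, and the descriptive TSQM-9 results remain valid as AR101-only summaries. The documents do not support saying that the whole model disappears, that the TSQM-9 has no usable analysis, or that any efficacy conclusion is weakened.

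**What to change.** Before database lock:

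1. Delete the TSQM-9 ANOVA sentence from SAP 9.6.1. An amendment or a Note to File will do: SAP 6.5 requires an amendment only when a principal feature changes.
2. Keep the descriptive statistics already planned for the nine items and three scales, and state that they cover AR101 subjects only, with the number contributing.
3. List any TSQM-9 response from a placebo subject; do not model it.

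The cost is a few lines of SAP text, with no new data, visit or protocol amendment. No planned information is lost, since a comparison would have needed placebo forms that the protocol does not schedule.

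Two optional side notes could go in at the same time. SAP 9.6.1 folds palatability into the exit survey ("The survey includes questions on study drug palatability, frequency of taking study drug as instructed"), although palatability is asked of both arms, so it would help to say which items have placebo answers. Protocol 6.5 unblinds each subject on completing the Exit Visit procedures, yet lists among those procedures questionnaires due after unblinding. That is a wording matter with no effect on the analysis, and it can wait for a later protocol amendment.
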